#### **6.2.25. Inflammatory Challenge Eligibility Checklist**

Eligibility for the Inflammatory Challenge will be determined at the beginning of the experimental visit to ensure participant safety immediately prior to the challenge.

#### **6.2.26. Locator Form**

The Locator Form asks participant to provide his/her name, address, and phone number and to provide names, addresses, and phone numbers of friends and family members who can be contacted if the subject cannot be located. This information is essential and will be collected during the initial screening, and will be updated throughout the study as necessary.

#### **6.2.27. MRI Screening Form**

The MRI Screening Form will be completed at the initial screening visit and again at the Inflammatory Challenge visit to ensure participant is safe to enter the scanner. The form provided by the Staglin Center for Cognitive Neuroscience and is required of anyone who enters the MR environment at the CCN.

#### **6.2.28. Medical History**

A Medical History interview will be conducted by the study physician or nurse practitioner at the medical screening visit and will screen for medical conditions that would make participation unsafe.

#### **6.2.29. Penn Alcohol Craving Scale (PACS)**

The PACS is a five-item, self-report measure that includes questions about the frequency, intensity, and duration of craving, the ability to resist drinking, and asks for an overall rating of craving for alcohol for the previous week. Each question is scaled from 0 to 6. Participants will complete this scale at initial screening, medical screening, and at the experimental visit.

#### **6.2.30. Physical Exam**

A physical examination of the oral cavity, head, eyes, ears, nose, and throat, cardiovascular system, lungs, abdomen, extremities, skin, neuropsychiatric mental status and sensory/motor status, musculoskeletal system and general appearance will be performed during the medical screening visit.

#### **6.2.31. Physical Sickness Symptoms Assessment**

Symptoms of physical sickness will be self-reported during each experimental visit on a scale from 0 (symptom not present) to 4 (very severe) at multiple time points (baseline, T1, T2, T3 and T4). At the baseline assessment, participants must have a total score below 10 in order to move forward with the experimental challenge. Scores of 10 or above will result in the visit being rescheduled when the participant is feeling better. Participants who rate any symptom as a '4' at the T1 – T4 assessment will be withdrawn from the study prior to the cue-reactivity paradigm. Research staff will contact the study physician and/or nurse practitioner on call to manage any severe sickness symptoms reported during the experimental session.

#### **6.2.32. Pittsburgh Sleep Quality Index (PSQI)**

The PSQI measures sleep quality using a 19-item questionnaire that will be self-administered electronically at the initial screening visit.

#### **6.2.33. Pregnancy Test**

An FDA approved rapid result urine pregnancy test will be used (i.e., dipstick test) to assess for pregnancy in female participants at each visit. If applicable, participants will be asked to sign a release of information form for study personnel to access medical records to obtain information regarding the outcome of a pregnancy that occurred during the study.

#### **6.2.34. Probabilistic Reward Task (PRT)**

A Probabilistic Reward Task (PRT) is a 25-minute task that will be administered at baseline and T2. The task assesses behavioral modulation as a function of reward-based reinforcement (i.e. reward seeking) by asking participants to respond to stimuli, eliciting a response bias by introducing an asymmetric reinforcer ratio.

#### **6.2.35. Profile of Mood States (POMS)**

The POMS measures dimensions of mood and will be completed electronically at screening and at 5 timepoints during the experimental visit (baseline, T1, T2, T3 and T4).

#### **6.2.36. Reasons for Heavy Drinking Questionnaire (RHDQ)**

The Reasons for Heavy Drinking Questionnaire (RHDQ) measures self-reported drinking motivation on two subscales (Reinforcement and Normalizing). The RHDQ will be completed at the initial screening visit.

#### **6.2.37. Reward, Relief, Habit Drinking Scale (RRHDS)**

The Reward, Relief, Habit Drinking Scale (RRHDS) categorizes subjects into reward, relief, or habit drinking subgroups. The RRHDS will be completed at the initial screening visit.

#### **6.2.38. Reward Responsiveness Scale (RRS)**

The RRS is a self-report questionnaire that measures reward responsiveness by asking subjects to rate their agreement with various statements on a 4-point Likert scale and will be administered at baseline and T2.

#### **6.2.39. Social Connection Measure**

The Social Connection Measure asks participants to identify a support figure that they could go to for help or comfort. Before the experimental study, participants are asked to rate on a 1-7 Likert scale how much they can rely on this support figure. The pre-study part of the measure will be administered at the medical screening visit.

During the experimental visit, participants are asked to rate on a 1-7 Likert scale how much they "feel like being around" their support figure at the time. This measure will be administered at baseline and T2.

#### **6.2.40. Social Disconnection Scale**

The Social Disconnection Scale asks participants to rate their agreement with 12 social connection/disconnection - related statements on a 1-5 Likert scale. This measure will be administered at baseline and T2.

#### **6.2.41. Structured Clinical Interview for DSM-5 Disorders (SCID-5)**

The SCID is a semi-structured interview for making the major DSM-5 diagnoses. The SCID screener assessment and alcohol module, used to assess current (past 12-month) AUD diagnosis will be completed by appropriately trained research personnel. Any positive responses on the SCID screener will be further assessed by the PI or designee to determine eligibility.

#### **6.2.42. Timeline Follow Back (TLFB)**

The Time Line Follow Back will be administered to assess quantity and frequency of alcohol, cigarette and marijuana use and will be completed at the initial screening (for the 30 days prior to that visit) and at each subsequent visit to gather data for every day prior to and including the last visit. Information obtained in this interview will be recorded on the TLFB Calendar and transcribed to the database.

#### **6.2.43. Toxicity Grading Scale Checklist**

Guidance document published by the US Department of Health and Human Services Food and Drug Administration titled "Toxicity Grading Scale for Healthy Adult and Adolescent Volunteers Enrolled in Preventive Vaccine Clinical Trials" will be used as a guideline for determining eligibility with regard to lab results and as part of the established study stopping protocol.

#### **6.2.44. Vital Signs**

Vital signs include sitting blood pressure, pulse rate (after sitting for at least 3 minutes), weight and body temperature. Values will be recorded on the visit checklist and entered into the database. Vital signs will be collected at screening and at 5 time points during the experimental visit (baseline, T1, T2, T3 and T4).

### **7. SAFETY MONITORING PLAN**

Safety monitoring will be conducted throughout the study; therefore safety concerns will be identified by continuous review of the data by the PI, medical personnel internal quality assurance checks, and DSMB.

#### **7.1. PI and Medical Personnel Safety Monitoring**

Participants will be given a 24-hour telephone number for calling the physician to discuss side effects, and physician office hours will be available as needed. Adverse events, including signs of sickness will be collected in an open-ended way at each in-person study visit. Vital signs will be monitored at multiple time points during the experimental study visit. Alcohol withdrawal will be monitored at each visit through administration of the CIWA, and any significant withdrawal, as indicated by a score of 8+ on the CIWA will be reported to the study physician and/or nurse

practitioner immediately. In the event that significant medical problems are encountered, the study blind will be broken and appropriate medical treatment will be provided.

### **7.2. Internal Quality Assurance Monitoring**

The PI will designate appropriately qualified personnel to periodically perform quality assurance checks at mutually convenient times during and after the study. These monitoring visits provide the opportunity to evaluate the progress of the study and to obtain information about potential problems. The monitor will assure that data are accurate and in agreement with any paper source documentation used, verify that subjects' consent for study participation has been properly obtained and documented, confirm that research subjects entered into the study meet inclusion and exclusion criteria, verify that study procedures are being conducted according to the protocol guidelines, monitor review AEs and SAEs, and assure that all essential documentation required by Good Clinical Practices (GCP) guidelines are appropriately filed. At the end of the study, they will confirm that the site has the appropriate essential documents on file, and advise on storage of study records.

### **7.3. Data and Safety Monitoring Board (DSMB)**

An independent DSMB of external advisors will meet prior to the start of the study, annually during enrollment and follow-up and at trial end to review safety data. The Board will be blinded to subjects' actual randomized group assignments but may request at any time that the blind be broken, if concerns arise from the blinded data. In addition to annual meetings, the DSMB will meet after half of the subjects (38) have been randomized to review safety data and the integrity of the study (i.e., an evaluation of the dropout rate and impact on the planned statistical analysis of the data) and make a formal recommendation to the PI on the continuation or early stopping of the study due to safety concerns. *Ad hoc* meetings will be convened if SAEs occur that are considered at least possibly related to the study procedures.

## **8. STATISTICAL METHODS AND POWER CONSIDERATIONS**

To confirm the efficacy of random assignment and to check for group equivalence across demographics, drinking history, and other relevant baseline measures we will perform one-way ANOVAs or Kruskal-Wallis tests on continuous variables and chi-square tests or Fisher's exact tests on categorical items. Descriptive statistics will be computed for continuous variables, and frequencies/proportions for categorical variables to summarize the data. Transformations of the continuous outcome variables will be performed as necessary (i.e. when data do not meet the assumptions of parametric statistical tests).

### **8.1. Statistical Power**

A power analysis was conducted for the study based on results from a previous human endotoxin challenge carried out in a control sample by our collaborators ([name] et al., 2010). Effect size was calculated based on [name] et al.'s reported sample size of  $N = 39$  and  $F$ -statistic of 8.13 for increase in negative mood at T2 after endotoxin infusion, yielding Cohen's  $d = 0.4687$ . Power analysis was conducted according to Cohen's guidelines to determine the sample size needed to achieve a power  $\geq 0.80$  (i.e. 80%) at an alpha level of .05. Using the program G\*Power version 3.1 and selecting the repeated measures ANOVA, within-between interactions design, where alpha = .05, effect size  $f = 0.234$ , we arrived at a total  $N = 76$  completers (38 heavy drinkers and 38 healthy controls). Specifically, we powered the study

to detect differences from baseline to peak (T2) inflammatory response, given that the remaining data points post-peak tend to be similar and may obscure the effects of the inflammatory challenge. Individuals who experience severe sickness symptoms will be excluded (expected to be <5% of the sample).

**8.2. Aim 1: To test that low dose endotoxin will increase cue-induced craving for alcohol in heavy drinkers as compared to light drinking controls, and as compared to placebo.**

Repeated measures analyses of variance (ANOVAs) will be conducted using PROC GLM in SAS Statistical Software. Specifically, in the repeated measures ANOVA models, Group (Heavy drinking versus light drinking) will be a two level between-subjects factor, Treatment (endotoxin vs. placebo) will be a two level between-subjects factor, and Cue (water cues versus alcohol cues) will be a between-subjects factor. The dependent measure will be self-reported alcohol craving captured by the Alcohol Craving Questionnaire. Sickness symptoms and drinking history (i.e., drinks per day and drinks per drinking day in past year) will be used as covariates in these analyses.

**8.3. Aim 2: To test whether low dose endotoxin (0.8 ng/kg of body weight) will increase depressed mood as compared to placebo.**

Repeated measures ANOVAs in which Group (Heavy drinking versus light drinking) will be a two level between-subjects factor, and Treatment (endotoxin vs. placebo) is a two level between-subjects factor. The outcome measure is depressed mood (captured by the POMS). Sickness symptoms and drinking history will also be included as covariates in these analyses.

**8.4. Exploratory Analysis: To test associations between plasma levels of proinflammatory cytokines (IL-6 and TNF- $\alpha$ ), depressed mood, and alcohol craving during the challenge; and examine sex differences in responses to the endotoxin challenge.**

Repeated measures ANOVAs will be used to capture the effects of Treatment (endotoxin vs. placebo) by Time (T0 to T2) for the proposed planned outcomes (i.e. proinflammatory cytokines, hourly craving scores) as well as models that include sex as a between-subjects factor. As with the primary aims, sickness symptoms and drinking history will be entered in these models as covariates.

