#### 5.4.4. Plasma Cytokine Assays

Whole blood samples will be collected in two lavender EDTA tubes at baseline and every hour for 4 hours post-infusion. After collection, the samples will be centrifuged at 4°C, plasma will be harvested into multiple aliquots, and then stored in a -70 °C freezer until the completion of the study. Peripheral markers of inflammation (TNF- $\alpha$ , IL-6, IL-8, IL-10, IFN $\gamma$ ) will be assessed using a multiplex assay.

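### Repeated-measures ANOVA in PROC GLM, with no missing-data rule, drops a participant's observed values for an outcome when one modelled value is missing; a mixed model would keep them

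*Combined protocol and SAP*

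**What the plan says.** Section 8.2 (Aim 1, cue-induced craving) states that "Repeated measures analyses of variance (ANOVAs) will be conducted using PROC GLM in SAS Statistical Software". Its factors are Group, Treatment and Cue. No Time factor is listed, although Section 5.4.5 runs the cue session at baseline and again at about two hours, with an urge rating after each three-minute period.

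Sections 8.3 (depressed mood), 8.4 (cytokines and hourly craving) and 8.6 (reward responsiveness) call for repeated-measures ANOVA without naming a procedure. Their time structure differs:

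- **8.3:** no Time factor or levels are given. Section 6.2.35 collects the POMS "at 5 timepoints during the experimental visit (baseline, T1, T2, T3 and T4").
- **8.4:** Time is limited to T0 to T2. The plan does not say whether T1 is a level. For the cytokines, Section 5.4.4 states that "Whole blood samples will be collected in two lavender EDTA tubes at baseline and every hour for 4 hours post-infusion".
- **8.6:** the reward task and the reward scale are given only at baseline and T2 (Sections 6.2.34 and 6.2.38).

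Section 8.1 says that the study was powered "to detect differences from baseline to peak (T2) inflammatory response". The reason it gives is that values after the peak resemble one another and could mask the effect.

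Sickness symptoms and drinking history are covariates in all four analyses. Section 5.4.1 replaces participants withdrawn for sickness. Nothing covers a single missing rating, questionnaire or sample in someone who stays in the study.

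**The concern.** PROC GLM with a REPEATED statement works on one row per participant and needs every repeated response in that row. One missing value removes the participant from the model, however many other values were recorded. The value at risk differs by section:

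- **8.2:** any one of the water or alcohol cue ratings.
- **8.3:** any POMS time that is modelled.
- **8.4:** T1, if T0 to T2 means three hourly levels, as well as T0 or T2.
- **8.6:** either member of the T0/T2 pair.

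Two things are at stake. The first is precision in a trial of 76. The second is the missingness assumption. A complete-case analysis is sound if loss depends only on treatment and the covariates in the model. A likelihood model also allows loss to depend on the participant's other recorded outcome values. Endotoxin is meant to produce symptoms, so arms could lose data unequally, though the documents give no figure for this.

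**Working it through.** **1. The plan's own sample size.** Inputs from Section 8.1: f = 0.234, alpha 0.05, power at least 0.80, G*Power's "selecting the repeated measures ANOVA, within-between interactions design" option, 76 "completers (38 heavy drinkers and 38 healthy controls"). The number of groups, the correlation between occasions (rho) and the sphericity correction are not stated. For k groups and m occasions, with sphericity assumed:

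- lambda = f² × N × m / (1 − rho)
- df1 = (k − 1)(m − 1)
- df2 = (N − k)(m − 1)

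With k = 2, m = 2 and rho = 0, the smallest N with power of at least 0.80 is 74 (power 0.802). Rounded up to four equal cells this is 4 × 19 = 76. At N = 76, lambda = 0.234² × 76 × 2 = 8.32 on 1 and 74 df, and power is 0.813. The stated 76 therefore fits a two-occasion calculation. With two groups, five occasions would need only 46 at rho = 0.

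**2. Participants lost to complete-case deletion.** The missing rate q per value is an assumption, taken as 1% to 5% and independent across values. With v values required by the model, the fraction lost is 1 − (1 − q)^v, and the number kept is 76 × (1 − q)^v.

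| Values required | Where it could apply | Lost, q = 1% | Lost, q = 5% | Kept of 76 |
|---|---|---|---|---|
| 2 | 8.6; 8.3 or 8.4 with T0 and T2 only; 8.2 with one cue session | 2.0% | 9.8% | 74.5 to 68.6 |
| 3 | 8.4 with T0, T1, T2 | 3.0% | 14.3% | 73.7 to 65.2 |
| 4 | 8.2 with two cues at T0 and T2 | 3.9% | 18.5% | 73.0 to 61.9 |
| 5 | 8.3 only, if all five times are modelled | 4.9% | 22.6% | 72.3 to 58.8 |

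**3. Sensitivity of power to N**, same formula, k = 2, m = 2:

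| N analysed | rho = 0 | rho = 0.25 | rho = 0.5 |
|---|---|---|---|
| 76 | 0.813 | 0.908 | 0.981 |
| 73 | 0.796 | 0.896 | 0.976 |
| 68 | 0.767 | 0.874 | 0.967 |
| 62 | 0.727 | 0.841 | 0.952 |

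At rho = 0, losing three participants takes power just below 0.80. These figures show how power for the planned baseline-to-T2 contrast moves with N. They are not the power of a three-, four- or five-value model.

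**The case against.** The strongest reply is that collecting data five times is not the same as analysing five times. A reader might infer from the hourly schedule that any missed hourly value deletes a participant with valid T0 and T2 data. The documents do not support that in general. In Section 8.4, T3 and T4 lie outside the stated Time range, so a missing value there deletes nobody. The cue paradigm and the Section 8.6 outcomes have no intermediate hourly value to lose. Section 8.3 leaves its levels open, and the rationale in Section 8.1 points to T0 and T2. This part of the reply stands.

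A reader might also put power at 70%, by taking the 58 participants left after five-value deletion at q = 5% and applying the two-occasion formula (0.697). That mixes two models. The same formula with m = 5 and rho = 0 gives 0.90 at N = 58.

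Other points stand in part:

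- PROC GLM is named only in Section 8.2, and no REPEATED statement is mentioned. In long format without REPEATED, only the affected row is dropped. That would, however, treat a participant's values as independent unless a participant term is added.
- The four-value model in Section 8.2 assumes that both cue sessions are modelled, whereas the text lists no Time factor.
- This is one supervised visit with an indwelling catheter and electronic questionnaires, so item-level loss may be small. If missing values cluster in the same participants, the loss is below the independent figures.
- Sickness is a planned covariate, so loss driven by sickness need not bias the complete-case estimate.
- PROC MIXED also drops records with a missing covariate.

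None of this supplies a missing-data rule, and replacing sickness withdrawals does not cover single missing values in those who remain.

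**Conclusion.** The point holds in a limited form. As specified, and if run with a REPEATED statement, the analysis discards observed data for an outcome when one modelled value is missing, and the plan has no rule for missing values. Under an assumed 1-5% independent missingness, the loss is about 2-10% of participants for two values, 3-14% for three and 4-18.5% for four. The 5-23% figure applies only if Aim 2 models all five POMS times, which the plan neither states nor excludes.

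The effect on power depends on a correlation that the plan does not give. It is thin at rho = 0 (0.813 falling to 0.767 at 68 participants) and comfortable at rho = 0.5 (0.952 even at 62). The documents do not establish that the trial is underpowered or that the treatment comparison is biased. They support a cheap improvement to the analysis and a request to state the time levels.

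**What to change.** In Sections 8.2 to 8.4 and 8.6:

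1. Fit the repeated-measures models in PROC MIXED (REML, unstructured within-participant covariance, Kenward-Roger degrees of freedom), with Cue and Time as within-participant factors where they apply. Section 8.2 now calls Cue between-subjects, although each participant receives both cues.
2. State the Time levels in each section, including whether Section 8.2 uses both cue sessions and whether T1 is a level in Section 8.4. In Section 8.3, make baseline to T2 the primary contrast.
3. Fix the time point of the sickness covariate and say what happens when it is missing, because the mixed model does not rescue those rows.
4. State that the primary analysis assumes missingness at random given the recorded values, and report missing values by arm.
5. Keep PROC GLM as a complete-case check.

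The cost is SAP wording and slightly more code, with no change to data collection. With complete data, the mean contrasts are essentially unchanged. The gain is largest where three or more values enter the model. For a two-value outcome, a participant with only one of the pair adds little information on change, so the gain there is modest.

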#### 5.4.5. Alcohol Cue Exposure

Participants will complete an alcohol cue-exposure paradigm at baseline (T0) during the experimental visit and again approximately 2 hours after receiving intravenous endotoxin (or matched placebo). Alcohol cue exposure will follow well-established experimental procedures. Sessions will begin with a 3-minute relaxation period. Participants will then hold and smell a glass of water for 3 minutes to control for the effects of simple exposure to any potable liquid. Next, participants will hold and smell a glass of their preferred alcoholic beverage for 3 minutes. Order is not counterbalanced because of carryover effects that are known to occur. Participants (who are smokers) will be allowed a smoke break immediately prior to and immediately after the CR assessment. After every 3 minute period, participants will rate their urge to drink on the Alcohol Urge Questionnaire.

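### Section 8.2 declares Cue a between-subjects factor and names a craving questionnaire the trial does not give, although every participant rates both cues on the AUQ; the primary craving model needs a text correction

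*Combined protocol and SAP*

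**What the plan says.** Section 8.2 gives the only written analysis for Primary Aim 1. It begins: "Repeated measures analyses of variance (ANOVAs) will be conducted using PROC GLM in SAS Statistical Software". It then lists three factors. Group (heavy or light drinking) is between-subjects. For Treatment, "Treatment (endotoxin vs. placebo) will be a two level between-subjects factor". For the third, "Cue (water cues versus alcohol cues) will be a between-subjects factor". No within-subject factor is named. The outcome sentence reads: "The dependent measure will be self-reported alcohol craving captured by the Alcohol Craving Questionnaire".

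Section 5.4.5 describes how the ratings arise. After a relaxation period, "Participants will then hold and smell a glass of water for 3 minutes". Then: "Next, participants will hold and smell a glass of their preferred alcoholic beverage for 3 minutes". After each three-minute period, "participants will rate their urge to drink on the Alcohol Urge Questionnaire". On the sequence of cues it says: "Order is not counterbalanced because of carryover effects that are known to occur". The paradigm is run at baseline (T0) and again about two hours after infusion (T2).

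Section 6.2.4 confirms that the AUQ is completed after each cue trial. The schedule in section 6.1 lists the AUQ and the Penn Alcohol Craving Scale. An Alcohol Craving Questionnaire appears neither there nor among the instrument descriptions in section 6.2.

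**The concern.** Cue varies within the person. The same participants are exposed to water and to alcohol, and the carryover argument for a fixed order makes sense only if one person receives both. Cue-induced craving is the alcohol-minus-water contrast, so the Cue interactions carry the Aim 1 hypothesis. A model with every factor between-subjects treats two ratings from one person as ratings from two people. Their correlation then goes into the wrong error term: too large for the cue interactions, and too small for the Treatment and Group main effects.

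The outcome name adds a second conflict. The schedule holds two craving scales, and section 8.2 names neither. An analyst would have to depart from the written plan to run a valid analysis, and a departure made after unblinding can look like a choice made on the results.

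**Working it through.** **The plan's sample size.** Section 8.1 gives N = 39, F = 8.13, an effect of 0.4687, f = 0.234, alpha .05, power of at least 0.80, and a within-between interaction design for T0 to T2.

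- Effect size, taking 39 − 2 = 37 error df: √(8.13/37) = 0.4688, and half of it is 0.234.
- Noncentrality: λ = f²·N·m/(1 − ρ). With N = 76, m = 2 measures and ρ = 0, λ = 0.234² × 76 × 2 = 8.32.
- Power at N = 76 is 0.813 for two groups (df 1, 74) and 0.812 for a one-df contrast over four cells (df 1, 72). The smallest N reaching 0.80 is 74 and 76 respectively.

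So N = 76 reproduces, but only with an unstated correlation of 0 or a similar unstated choice: two groups with ρ = 0.5 would need 38, and four groups with 3 df give 76 at ρ of about 0.28 to 0.30. The calculation already assumes a repeated factor, so correcting section 8.2 does not change N.

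**The literal model against the correct one.** Assumptions: one cue session; two ratings per person; 19 people in each Group x Treatment cell (76/4; the allocation ratio is not stated); equal rating variance σ²; within-person correlation ρ from 0.3 to 0.8 (the documents give none); no covariates.

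- Literal model: 152 ratings in 8 cells, error df 152 − 8 = 144, critical F = 3.907, error variance about σ².
- Cue within-subject: error df 76 − 4 = 72, critical F = 3.974.
- The Treatment x Cue coefficient has true variance σ²(1 − ρ)/(2N), but the literal model uses σ²/(2N). Its F is therefore about (1 − ρ) times a chi-square on 1 df, and type I error is about P(χ²₁ > 3.907/(1 − ρ)). At ρ = 0.5 the threshold is 7.81, giving 0.005.
- The Treatment main effect has true variance σ²(1 + ρ)/(2N), so its type I error is about P(χ²₁ > 3.907/(1 + ρ)). At ρ = 0.5 the threshold is 2.60, giving 0.107.

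Power is shown for two effects. The first is the plan's f = 0.234, for which λ = 8.32/(1 − ρ). The second is an arm difference of 0.65 SD of the alcohol-minus-water score, for which λ = 0.65² × 38/2 = 8.03; the correct test detects it with power of about 0.80 at every ρ.

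Simulation (20,000 or more trials per setting; the closed forms agree closely):

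| ρ (assumed) | 0.3 | 0.5 | 0.7 | 0.8 |
|---|---|---|---|---|
| Treatment x Cue, type I error, literal | 0.020 | 0.006 | 0.0005 | <0.0001 |
| Treatment x Cue, type I error, Cue within | 0.049 | 0.050 | 0.049 | 0.047 |
| Power at f = 0.234, literal | 0.86 | 0.90 | 0.95 | 0.97 |
| Power at f = 0.234, Cue within | 0.93 | 0.98 | >0.99 | >0.99 |
| Power at 0.65 SD of difference, literal | 0.68 | 0.52 | 0.23 | 0.07 |
| Power at 0.65 SD of difference, Cue within | 0.80 | 0.80 | 0.80 | 0.80 |
| Treatment main effect, type I error, literal | 0.085 | 0.109 | 0.133 | 0.145 |

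The two power comparisons differ because f = 0.234 holds the effect fixed in rating SDs: the arms differ by 4 × 0.234 = 0.94 rating SDs in alcohol minus water. The second effect shrinks as ρ rises. It is 0.65 × √(2(1 − ρ)) rating SDs, or 0.77, 0.65, 0.50 and 0.41 across the table.

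**The case against.** The strongest reply is that this is a one-word slip. Section 8.2 calls the model repeated measures, and section 8.1 used a within-between design; a wholly between-subjects model contradicts both. Sections 8.3 and 8.6 also announce repeated measures while listing only Group and Treatment, so the plan tends to leave its repeated factor unstated. Section 8.4 does name Time (T0 to T2), and Time may be implied in Aim 1 as well. This stands. A reader might infer that the primary test will use the wrong error term; the documents show only that it would if the sentence were followed literally.

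The size also depends on calibration. At the only effect size the plan gives, literal power stays above 0.80 throughout. That f was derived for negative mood, so for craving it is only a reference point. The fall to 0.07 belongs to a smaller effect and a high assumed correlation. The layout of two ratings per person is also a simplification, since the protocol collects two cue sessions.

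A reader might further infer that the primary finding is exposed to false positives. It is not: the inflation falls on the Treatment main effect averaged over water and alcohol, and the cue-induced contrast is tested conservatively.

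On the instrument, the AUQ is the only questionnaire given after each cue period, and the Penn scale covers the previous week (section 6.2.29). The wrong name is therefore unlikely to change which data are analysed. What remains is that the sole specification of the primary craving analysis conflicts with the procedures on both its factor and its outcome.

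**Conclusion.** Section 8.2 is wrong as written on two points, the status of Cue and the name of the outcome. Both are probably drafting slips, and the statistical harm is conditional on running the text literally. Under the stated assumptions (one session, 19 per cell, ρ 0.3 to 0.8), the Treatment x Cue test would then have type I error of 0.02 to below 0.0001 instead of 0.05. It would lose about 3 to 8 power points at f = 0.234, and would drop from 0.80 to between 0.68 and 0.07 for an effect the correct test detects with 80% power. The Treatment main effect would have type I error of about 0.09 to 0.14. A reader might conclude that the trial is too small; the documents do not support that, because the calculation behind N = 76 already assumes a within-between design.

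**What to change.** In section 8.2, declare Cue (water, alcohol) a two-level within-subject factor and name the AUQ as the dependent measure.

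Those two edits leave open how the two cue sessions are used. The paradigm runs at T0 and about T2, and power was computed for T0 to T2, so section 8.2 should also include Time (T0, T2) as a within-subject factor. To the same end, it could analyse the T2 alcohol-minus-water AUQ difference adjusted for the T0 difference, with Treatment, Group and Treatment x Group. It should state which term tests the aim: Treatment x Cue x Time in the full model, or the Treatment term in the difference model, with Group added to that interaction for the heavy-versus-light comparison.

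The cost is text edits only, ideally before unblinding. Data, procedures and sample size are unchanged.
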